After the participant expectorates the mouth rinse, research staff will collect another salivary sample (T_0 , 2 mL over 5 min). During a 10 min recuperation period, the study participants will answer demographics survey questions and questions regarding the taste, color, flavor and general acceptability of using the mouthrinse as part of routine dental and medical visits. At 15 minutes post-rinse, the participant will be asked to provide an additional saliva sample (2 mL over 5 min), followed by another 10-minute recuperation period. This sequence will be repeated for the 30, 45- and 60-minute time points post-rinse. At 60 minutes, the study participant will give their final salivary sample (2 mL over 5 min).

The samples will be stored and used for determining SARS-CoV-2 viral load by RT-PCR and inflammation-associated cytokine and chemokine concentration (pg/mL). The impact of mouthrinses on viral load in samples will be using a Relative quantification (RQ) ratio. A cycle threshold cut off (see sections 9.4-9.5) of 22 will be used for determining which samples will be used in downstream viral infectivity assays. Viral infectivity will be calculated (see sections 9.4-9.5) and yield a Reduction Factor as quantified output. Peripheral blood will be collected at the end of salivary collection (2 - 5 mL in EDTA-containing blood collection tubes).

Participants will be provided materials and oral hygiene instruction related to daily use of oral hygiene products provided by the study. During the week between study visits, participants will be directed to brush with Colgate toothpaste (at least twice per day) and rinse with the Colgate mouthrinse according to on-label instructions (10-20 mL, 30-60 seconds, 2-3 times per day depending on mouthrinse).

Participants will be asked to keep a daily diary of oral hygiene performance, product usage, COVID-19 symptoms and exposures. Participants will be given a \$30 gift card for their participation in visit 1. Participants will be scheduled to return to the GoHealth Clinical Research Unit at one week after the baseline assessment, during which additional salivary (1 time point, 2 mL

of saliva over 5 min, no rinse will occur) and blood samples (2 - 5 mL in EDTA-containing blood collection tubes) will be collected.

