4. SELECTION AND ENROLLMENT OF PARTICIPANTS

4.1 Inclusion Criteria

Subjects must meet all of the following inclusion criteria to be eligible for enrollment in the study:

- Diagnosed SARS-CoV-2+ status. Either became symptomatic in the prior 7 days, or if not symptomatic, likely infected/exposed within the prior 7 days. All patients listed from the UNC Respiratory Diagnostic Center (RDC) have a confirmed SARS-CoV-2 infection and have consented to be contacted for research purposes. For patients contacting study coordinators for enrollment, who were not tested in the RDC, they must provide written proof of positive SARS-CoV-2 status in the prior 7 days.
- Individuals (all sex, all gender) at least 18 y.o.a. and at most 65 y.o.a. and in good oral health without any known allergies to commercial dental products or cosmetics. ASA class I or II prior to SARS-CoV-2 infection.
- Evidence of a personally signed and dated informed consent document indicating the subject (or legally acceptable representative) has been informed of all pertinent aspects of the trial and all of their questions have been answered.
- Able to comprehend and follow the requirements of the study (including availability on scheduled visit dates) based on research site personnel’s assessment.

- Females of childbearing potential will have a negative urine pregnancy test (on site) or be physically incapable of pregnancy (implants or injections, Intrauterine device, Bilateral tubal ligation, Hysterectomy, Ovariectomy, Women post-menopausal)

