4.2 Exclusion Criteria

Subjects presenting with any of the following will not be included in the study:

- Patients who have been eating or drinking within an hour of the study
- Patients under 18 y.o.a. and older than 65 y.o.a.
- Subjects presenting with and/or self-reporting any of the following will not be included in the study:
 - history of significant adverse effects following use of oral hygiene products such as toothpastes and mouthrinses. (self-reported)
 - Self-reported allergy to hydrogen peroxide, peroxy, chlorhexidine gluconate, perigard, peridex, colgate total zero, colgate total, cetylpyridinium chloride, essential oils (Eucalyptol, Menthol, Methyl salicylate, Thymol), and other components in the mouth rinses (methyl salicylate, ethanol, saccharin sodium, glycerin, propylene glycol, sorbitol, FD&C blue no. 1, Poloxamer 407, Benzoic acid, Zinc chloride, Sodium benzoate, Sucralose, PEG-40 sorbitan diisostearate, potassium sorbate, citric acid).
 - History of serious medical conditions that, at the discretion of the Investigator, will disqualify the subject. (Self-reported)
 - A history of severe dry mouth (xerostomia), severe drug-induced xerostomia (antidepressants, anticonvulsants, antihypertensives), or Sjogren's syndrome
 - A history of recent (within the last 30 days) or current **recent oral herpes flare up**, candida (thrush) infection, aphous ulcer flare up, current/active severe periodontal disease, or other recent oral viral infection or flare up within the past 30 days (self-reported)
 - Current history of alcohol or drug abuse (self-reported).
 - History of drinking water or eating food within an hour of the study visit.
 - History of drinking alcohol within 12 hours of the study visit.
 - History of using a commercial mouthrinse within 24 hours of the study visit.
 - Participation in any study involving oral care products, concurrently or within the previous 30 days. (self-reported)
 - Positive pregnancy test reported pregnancy or lactation (this criterion is due to oral tissue changes related to pregnancy and nursing which can affect interpretation of study results. Additionally, women are advised to check with their physician before using Chlorhexidine Gluconate during pregnancy and lactation, which cannot occur in a blinded, randomized trial.)

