 - Other severe acute or chronic medical or psychiatric conditions or laboratory abnormality that may increase the risk associated with trial participation or investigational product administration or may interfere with the interpretation of trial results and, in the judgment of the Investigator, would make the subject inappropriate for entry into this trial.
 - Patient with developmental/cognitive disability that cannot self-consent, comprehend and follow the requirements of the study based on research site personnel's assessment.
 - Patients with sizable mucosal tears, abrasions, growths or burns in the mouth
 - Patients with kidney dysfunction

The following table lists exclusion criteria specific to each mouth rinse proposed in the study:

Mouthrinse*	Exclusions
1.5% w/v hydrogen peroxide rinse (Peroxyl)	
 • Pregnancy and lactation 
 ◦ Although there is not sufficient specific clinical data on the use of 1.5 % w/v hydrogen peroxide rinse in this patient group, self-administration without medical advice is not recommended. • Do not use in children under 12

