0.12% Chlorhexidine Gluconate (Periogard)	
 • Carcinogenesis, Mutagenesis, Impairment of Fertility 
 ◦ In a drinking water study in rats, carcinogenic effects were not observed at doses up to 38 mg/kg/day. Mutagenic effects were not observed in two mammalian in vivo mutagenesis studies with chlorhexidine gluconate. The highest doses of chlorhexidine used in a mouse dominant-lethal assay and a hamster cytogenetics test were 1000 mg/kg/day and 250 mg/kg/day, respectively. No evidence of impaired fertility was observed in rats at doses up to 100 mg/kg/day. • Pregnancy: Teratogenic Effects 
 ◦ Reproduction studies have been performed in rats and rabbits at chlorhexidine gluconate doses up to 300 mg/kg/day and 40 mg/kg/day, respectively, and have not revealed evidence of harm to the fetus. However, adequate and well-controlled studies in pregnant women have not been done. Because animal reproduction studies are not always predictive of human response, this drug should be used during pregnancy only if clearly needed. • Nursing Mothers 
 ◦ It is not known whether this drug is excreted in human milk. Because many drugs are excreted in human milk, caution should be exercised when 0.12% Chlorhexidine Gluconate is administered to a nursing woman. In parturition and lactation studies with rats, no evidence of impaired parturition or of toxic effects to suckling pups was observed when chlorhexidine gluconate was administered to dams at doses up to 100 mg/kg/day. • Pediatric Use 
 ◦ Clinical effectiveness and safety of 0.12% Chlorhexidine Gluconate have not been established in children under the age of 18.
1 st : Peroxyl 2 nd : Periogard	
 • No additional exclusions from sequential use are documented. • Please see above for adverse effects of each rinse individually.
0.075% Cetylpyridinium Chloride (Colgate Total Zero)	
 • Do not use in children under 6
Sterile Water	
No contraindications

**All mouthrinses are commercially available in the USA, routinely used in clinical settings, and will be used in an on-label manner.*

Summary of Inclusion and Exclusion Criteria for Mouthrinse RCT

Inclusion Criteria	Exclusion Criteria

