Individuals (all sex, all gender) at least 18 years of age and at most 65 years of age in good oral health and with stable physical health (ASA Class I or II prior to SARS-CoV-2 infection), decided at the discretion of the study coordinator.	Known allergies or significant adverse reactions following the use of oral hygiene products (toothpastes, mouthrinses), commercial cosmetics, and any ingredient in the mouthrinses (list will be provided).
Diagnosed SARS-CoV-2+ status (within the past 48 hours) who became symptomatic in the prior 7 days, or if not symptomatic, was likely infected/exposed within the prior 7 days.	Established history of severe Xerostomia (drug-induced or autoimmune dry mouth), renal disease, Hepatitis C Virus (HCV), severe periodontal disease with actively bleeding gums, significant oral abrasions/ulcers or growths, current alcohol abuse, and/or current recreational drug abuse. Other severe acute or chronic medical or psychiatric conditions or laboratory abnormality that may increase the risk associated with trial participation or investigational product administration or may interfere with the interpretation of trial results and, in the judgment of the Investigator, would make the subject inappropriate for entry into this trial.
Evidence of a personally signed and dated informed consent document indicating the subject (or legally acceptable representative) has been informed of all pertinent aspects of the trial and all of their questions have been answered.	Drinking or eating within an hour of the study visit. Consuming alcohol within 12 hours of the study visit. Rinsing with a commercial mouthrinse within 24 hours of the study visit.
Able to comprehend and follow the requirements of the study (including availability on scheduled visit dates) based on research site personnel's assessment.	Developmental/cognitive disability such that the participant cannot self-consent, comprehend and follow the requirements of the study based on research site personnel's assessment.
Females of childbearing potential will have a negative urine pregnancy test (on site) or be physically incapable of pregnancy (implants or injections, Intrauterine device, Bilateral tubal ligation, Hysterectomy, Ovariectomy, Women post-menopausal)	Positive pregnancy test, reported pregnancy or lactation.

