4.3 Study Enrollment Procedures

Outpatient subjects will be recruited from patients seen in the UNC Respiratory Diagnostic Center (RDC) who have tested positive for SARS-CoV-2+ and consented to be contacted for participation in COVID-related research studies. The potential subjects will have signed a prior facility consent at the RDC confirming their willingness to share their name and contact information to be contacted for study participation in COVID-19 related research. We will not receive information on subjects that decline this internal consent. A brief review of the patient's Epic chart will take place for medical screening and to identify any missing contact information, as needed. Subjects will be contacted for recruitment by phone and (if unreachable by phone) by secure email by study personnel; patients will have the study rationale and risks explained and will be provided time to ask questions and consider participation. If patients are interested in participating, both appointments will be scheduled for them at the Adams School of Dentistry Go Health Clinical research core. Consent documentation will be signed in person and in private in the Go Health Clinical Research Core.

For Spanish speaking patients and/or parents, Spanish forms will be provided and communication will occur through a Spanish translator. All patients are adults and over normal cognitive capacity, and therefore will be able to consent for themselves. A list of SARS-CoV-2+ subjects that have consented to be contacted for research, will be provided by the RDC clinic, sent via secure UNC servers or secure UNC email to our research team's clinical coordinator, and this list will include names and contact details (PHI). This list is updated daily and provided to approved research sites, including ours.

At the visit, a consented patient will answer screening questions regarding inclusion and exclusion criteria. Answers will be entered into the CDART research database managed by UNC. Prior to finalizing these screening questions, women participants of childbearing potential will be asked to provide a urine sample in the restroom, to undergo a rapid pregnancy test by study personnel. Any pregnant or lactating patients will be excluded.

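### The eligibility criterion counts users of implants, injections and intrauterine devices as unable to become pregnant, so they can qualify without a pregnancy test

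*Combined protocol and SAP*

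**What the plan says.** The inclusion criterion in section 4.1 opens with the test: "Females of childbearing potential will have a negative urine pregnancy test (on site"). It then gives an alternative: "or be physically incapable of pregnancy (implants or injections, Intrauterine device, Bilateral tubal ligation, Hysterectomy, Ovariectomy, Women post-menopausal"). The summary table of inclusion and exclusion criteria, which follows section 4.2, has the same alternative, again beginning "or be physically incapable of pregnancy (implants or injections, Intrauterine device".

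Other parts of the protocol that bear on this:

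- **Exclusion (section 4.2).** The matching exclusion reads "Positive pregnancy test reported pregnancy or lactation". Two reasons are given: pregnancy changes oral tissue in ways that could affect interpretation, and the physician check advised before chlorhexidine use cannot take place in a blinded trial.
- **Screening procedure (sections 4.3, 6.2.1 and 12.2).** All three say that "women participants of childbearing potential will be asked to provide a urine sample in the restroom, to undergo a rapid pregnancy test". None defines childbearing potential.
- **Schedule (section 6.1).** A urine pregnancy analysis is marked at Visit 1, with no note on who takes it.
- **Rinse-specific cautions (table in section 4.2).** For Peroxyl in pregnancy and lactation, "self-administration without medical advice is not recommended". For Periogard, "this drug should be used during pregnancy only if clearly needed".
- **Home use (section 3).** Between visits participants are to "rinse with the Colgate mouthrinse according to on-label instructions (10-20 mL, 30-60 seconds, 2-3 times per day depending on mouthrinse"). The Précis exempts controls.

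**The concern.** The list mixes two different kinds of entry. Hysterectomy, ovary removal, tubal ligation and menopause are surgical or permanent states. An implant, an injection or an intrauterine device lowers the chance of pregnancy for as long as it is in use and working. Placing the second kind under a heading meant for women who cannot conceive is a factual error in the criterion, and it carries a consequence because that heading is an alternative to the test.

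The plan excludes pregnancy deliberately, and the urine test is its only means of finding a pregnancy the participant does not know about. A woman wrongly exempted could be randomised to a rinse whose own entry in the protocol advises caution in pregnancy, and then use it unsupervised at home for a week. This is a participant-safety point. It does not touch the estimates, the power or the primary conclusions.

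**Working it through.** The plan gives no figure on this point, so there is none to reproduce. The check is first a reading of the text, then a rough bound on the size.

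**1. Does any other passage close the gap?** Take a woman with an intrauterine device who is pregnant and does not know it.

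| Place | What it does for her |
|---|---|
| Section 4.1 and the summary table | She satisfies the criterion through the second route; no test needed |
| Section 4.2 exclusion | Triggered by a positive test or a reported pregnancy; she has neither |
| Sections 4.3, 6.2.1, 12.2 | Tested if she counts as being of childbearing potential; the term is undefined |
| Section 6.1 | Test scheduled at Visit 1; does not say for whom |

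On the ordinary meaning of childbearing potential she is tested. But the list in section 4.1 is the only place that says who need not be, and staff who follow it would pass her without a test. The text leaves the conflict unresolved.

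**2. Which arms carry a caution?** Peroxyl, Periogard and the sequential Peroxyl–Periogard arm: 3 of 5, or 0.6. The rinse-specific table gives no pregnancy caution for cetylpyridinium chloride or sterile water.

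**3. How many undetected pregnancies?** The only input from the documents is enrolment of 30 per arm in five arms (section 3): 30 × 5 = 150. The rest are assumptions, because the documents give no sex split, contraceptive use, failure rate or detection window:

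- half the participants are women: 75;
- 20% to 40% of them use an implant, injection or intrauterine device;
- annual failure is 0.1% to 4%;
- a pregnancy goes unnoticed for one month, i.e. 1/12 of a year.

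Expected number = women × proportion using these methods × annual failure × 1/12.

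| Case | Calculation | All arms | Three cautioned arms (× 0.6) |
|---|---|---|---|
| Screening text governs | all such women tested | 0 | 0 |
| Section 4.1 followed, low | 75 × 0.20 × 0.001 / 12 | 0.00125 | 0.00075 |
| Section 4.1 followed, high | 75 × 0.40 × 0.04 / 12 | 0.10 | 0.06 |
| Extreme ceiling: all 150 are women using these methods | 150 × 1.0 × 0.04 / 12 | 0.5 | 0.3 |

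Even the ceiling is below one pregnancy in the whole trial.

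**The case against.** The strongest reply is that the operating procedure already deals with this. Three sections require the urine test for women of childbearing potential without exempting contraceptive users, they place it before the screening questions are finalised, and section 4.3 puts randomisation after eligibility is confirmed. In ordinary clinical use a woman with an implant or an intrauterine device is of childbearing potential. The grammar of section 4.1 points the same way, since the listed women are introduced as a subset of that group. This has force: the documents do not show that such women will go untested, and the finding should not be read as saying so. It is not decisive, because the same literal reading would also send women after hysterectomy for testing, and nothing says that the screening text overrides the list.

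The harm is also weakly supported. The Periogard entry reports rat and rabbit studies without evidence of fetal harm, the Peroxyl entry cites a lack of clinical data rather than a known hazard, and the products are marketed, used on-label and spat out. The size estimate rests on assumed rates. All of this stands, and it keeps the point minor.

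Finally, deleting the three methods does not by itself define childbearing potential. That is fair, and a definition is worth adding.

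**Conclusion.** The criterion is wrong as written, in both places where it appears. That conclusion rests on the text alone and is firm. Whether any woman would actually be randomised untested is uncertain, because it depends on whether staff follow the eligibility list or the screening procedure.

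The practical effect is very small: nil on one reading and, on the other, an expected count of at most about 0.1 under the working assumptions on sex split, contraceptive use, failure rate and detection window. No sample size, estimate or test in the plan changes. This is a minor safety and drafting defect, worth correcting because pregnancy is an explicit exclusion and the correction is nearly free.

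**What to change.** Remove implants, injections and intrauterine device from the bracketed list in section 4.1 and in the summary table. What remains is surgical sterilisation and menopause, and women using the reversible methods then need the negative on-site test.

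To settle the undefined term, add one sentence defining a woman of childbearing potential as any woman who is neither surgically sterile nor post-menopausal, and use that definition in sections 4.3, 6.2.1 and 12.2.

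The cost is a wording change in two places, one optional definition, and a few more urine strips at a Visit 1 step that already exists. Sample size, timetable and analysis are unaffected.

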4.2 Exclusion Criteria

Subjects presenting with any of the following will not be included in the study:

- Patients who have been eating or drinking within an hour of the study
- Patients under 18 y.o.a. and older than 65 y.o.a.
- Subjects presenting with and/or self-reporting any of the following will not be included in the study:
 - history of significant adverse effects following use of oral hygiene products such as toothpastes and mouthrinses. (self-reported)
 - Self-reported allergy to hydrogen peroxide, peroxy, chlorhexidine gluconate, perigard, peridex, colgate total zero, colgate total, cetylpyridinium chloride, essential oils (Eucalyptol, Menthol, Methyl salicylate, Thymol), and other components in the mouth rinses (methyl salicylate, ethanol, saccharin sodium, glycerin, propylene glycol, sorbitol, FD&C blue no. 1, Poloxamer 407, Benzoic acid, Zinc chloride, Sodium benzoate, Sucralose, PEG-40 sorbitan diisostearate, potassium sorbate, citric acid).
 - History of serious medical conditions that, at the discretion of the Investigator, will disqualify the subject. (Self-reported)
 - A history of severe dry mouth (xerostomia), severe drug-induced xerostomia (antidepressants, anticonvulsants, antihypertensives), or Sjogren's syndrome
 - A history of recent (within the last 30 days) or current **recent oral herpes flare up**, candida (thrush) infection, aphous ulcer flare up, current/active severe periodontal disease, or other recent oral viral infection or flare up within the past 30 days (self-reported)
 - Current history of alcohol or drug abuse (self-reported).
 - History of drinking water or eating food within an hour of the study visit.
 - History of drinking alcohol within 12 hours of the study visit.
 - History of using a commercial mouthrinse within 24 hours of the study visit.
 - Participation in any study involving oral care products, concurrently or within the previous 30 days. (self-reported)
 - Positive pregnancy test reported pregnancy or lactation (this criterion is due to oral tissue changes related to pregnancy and nursing which can affect interpretation of study results. Additionally, women are advised to check with their physician before using Chlorhexidine Gluconate during pregnancy and lactation, which cannot occur in a blinded, randomized trial.)
 - Other severe acute or chronic medical or psychiatric conditions or laboratory abnormality that may increase the risk associated with trial participation or investigational product administration or may interfere with the interpretation of trial results and, in the judgment of the Investigator, would make the subject inappropriate for entry into this trial.
 - Patient with developmental/cognitive disability that cannot self-consent, comprehend and follow the requirements of the study based on research site personnel's assessment.
 - Patients with sizable mucosal tears, abrasions, growths or burns in the mouth
 - Patients with kidney dysfunction

The following table lists exclusion criteria specific to each mouth rinse proposed in the study:

Mouthrinse*	Exclusions
1.5% w/v hydrogen peroxide rinse (Peroxyl)	
 • Pregnancy and lactation 
 ◦ Although there is not sufficient specific clinical data on the use of 1.5 % w/v hydrogen peroxide rinse in this patient group, self-administration without medical advice is not recommended. • Do not use in children under 12
0.12% Chlorhexidine Gluconate (Periogard)	
 • Carcinogenesis, Mutagenesis, Impairment of Fertility 
 ◦ In a drinking water study in rats, carcinogenic effects were not observed at doses up to 38 mg/kg/day. Mutagenic effects were not observed in two mammalian in vivo mutagenesis studies with chlorhexidine gluconate. The highest doses of chlorhexidine used in a mouse dominant-lethal assay and a hamster cytogenetics test were 1000 mg/kg/day and 250 mg/kg/day, respectively. No evidence of impaired fertility was observed in rats at doses up to 100 mg/kg/day. • Pregnancy: Teratogenic Effects 
 ◦ Reproduction studies have been performed in rats and rabbits at chlorhexidine gluconate doses up to 300 mg/kg/day and 40 mg/kg/day, respectively, and have not revealed evidence of harm to the fetus. However, adequate and well-controlled studies in pregnant women have not been done. Because animal reproduction studies are not always predictive of human response, this drug should be used during pregnancy only if clearly needed. • Nursing Mothers 
 ◦ It is not known whether this drug is excreted in human milk. Because many drugs are excreted in human milk, caution should be exercised when 0.12% Chlorhexidine Gluconate is administered to a nursing woman. In parturition and lactation studies with rats, no evidence of impaired parturition or of toxic effects to suckling pups was observed when chlorhexidine gluconate was administered to dams at doses up to 100 mg/kg/day. • Pediatric Use 
 ◦ Clinical effectiveness and safety of 0.12% Chlorhexidine Gluconate have not been established in children under the age of 18.
1 st : Peroxyl 2 nd : Periogard	
 • No additional exclusions from sequential use are documented. • Please see above for adverse effects of each rinse individually.
0.075% Cetylpyridinium Chloride (Colgate Total Zero)	
 • Do not use in children under 6
Sterile Water	
No contraindications

**All mouthrinses are commercially available in the USA, routinely used in clinical settings, and will be used in an on-label manner.*

Summary of Inclusion and Exclusion Criteria for Mouthrinse RCT

Inclusion Criteria	Exclusion Criteria
Individuals (all sex, all gender) at least 18 years of age and at most 65 years of age in good oral health and with stable physical health (ASA Class I or II prior to SARS-CoV-2 infection), decided at the discretion of the study coordinator.	Known allergies or significant adverse reactions following the use of oral hygiene products (toothpastes, mouthrinses), commercial cosmetics, and any ingredient in the mouthrinses (list will be provided).
Diagnosed SARS-CoV-2+ status (within the past 48 hours) who became symptomatic in the prior 7 days, or if not symptomatic, was likely infected/exposed within the prior 7 days.	Established history of severe Xerostomia (drug-induced or autoimmune dry mouth), renal disease, Hepatitis C Virus (HCV), severe periodontal disease with actively bleeding gums, significant oral abrasions/ulcers or growths, current alcohol abuse, and/or current recreational drug abuse. Other severe acute or chronic medical or psychiatric conditions or laboratory abnormality that may increase the risk associated with trial participation or investigational product administration or may interfere with the interpretation of trial results and, in the judgment of the Investigator, would make the subject inappropriate for entry into this trial.
Evidence of a personally signed and dated informed consent document indicating the subject (or legally acceptable representative) has been informed of all pertinent aspects of the trial and all of their questions have been answered.	Drinking or eating within an hour of the study visit. Consuming alcohol within 12 hours of the study visit. Rinsing with a commercial mouthrinse within 24 hours of the study visit.
Able to comprehend and follow the requirements of the study (including availability on scheduled visit dates) based on research site personnel's assessment.	Developmental/cognitive disability such that the participant cannot self-consent, comprehend and follow the requirements of the study based on research site personnel's assessment.
Females of childbearing potential will have a negative urine pregnancy test (on site) or be physically incapable of pregnancy (implants or injections, Intrauterine device, Bilateral tubal ligation, Hysterectomy, Ovariectomy, Women post-menopausal)	Positive pregnancy test, reported pregnancy or lactation.
	A history of recent (within the last 30 days) or current recent oral herpes flare up, candida (thrush) infection, aphous ulcer flare up, current/active severe periodontal disease with bleeding gums, or other recent oral viral infection or flare up within the past 30 days.

